### 4.2 Study Endpoints

#### 4.2.1 Primary Study Endpoints

The null hypothesis for the primary feasibility objective is that 75% of the subjects will successfully complete ferumoxytol injection treatment as per study protocol.

#### 4.2.2 Secondary Study Endpoints

Primary Safety Endpoint: The incidence of treatment-related adverse events

#### 4.2.3 Exploratory Endpoints

- Change from pre-treatment baseline in serum ferritin 2-24 weeks after ferumoxytol injection therapy
- Change from pre-treatment baseline in transferrin saturation 2-24 weeks after ferumoxytol injection therapy
- Change from pre-treatment baseline in hemoglobin level 2-24 weeks after ferumoxytol injection therapy
- Change from pre-treatment baseline in 6-minute walk distance 2-24 weeks after ferumoxytol injection therapy

## 5 Study Enrollment and Withdrawal

### 5.1 Inclusion Criteria

In order to be eligible to participate in this study, an individual must meet all of the following criteria:

- Age >18 years
- Status post placement of durable ventricular assist device with stable clinical status for >30days
- Hemoglobin >6 g/dL AND <13 g/dL (men) or <12 g/dL (women) within last 90 days
- Serum ferritin <100 ng/mL OR Serum ferritin 100-299 ng/mL with transferrin saturation <20% within last 90 days
- Able and willing to provide written informed consent

### 5.2 Exclusion Criteria

An individual who meets any of the following criteria will be excluded from participation in this study:

- Known hypersensitivity to Ferumoxytol injection or other intravenous iron preparation

CONFIDENTIAL

This material is the property of the NYU School of Medicine and Langone Medical Center. Do not disclose or use except as authorized in writing by the study sponsor  
Interventional Template Version: 28 APR 2017

- History of anaphylaxis
- Treatment with erythropoiesis stimulating agent or intravenous iron in last 3 months
- Renal failure on hemodialysis
- Respiratory failure on mechanical ventilation
- Disabling Stroke
- Ventricular assist device thrombosis
- Evidence of active gastrointestinal bleeding or other active blood loss
- Hospitalization <30 days
- Pregnant or breastfeeding women

### **5.3 Vulnerable Subjects**

There will be no vulnerable subjects enrolled in this study.

### **5.4 Strategies for Recruitment and Retention**

Study participants will be recruited from the population of 40-50 VAD patients followed at NYULH. These patients are followed by a dedicated multidisciplinary VAD team at regular intervals as outpatients. Assessment of iron deficiency anemia and 6-minute walk testing are standard of care during follow-up in these patients, and iron-deficient patients are routinely referred for intravenous iron infusions as part of standard clinical care. Participation in the study differs from clinical care only in the formulation of intravenous iron and the location of the iron infusion. Clinical staff in the outpatient VAD clinic will assess patient interest in participation in the study and will inform study personnel. Trained study personnel will obtain consent in a private quiet setting at the NYU CTSI at a time of clinical stability.

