## Schematic of Study Design

## Schedule of Assessments

| Visit Name                  | Screening   | First Dose Ferumoxytol injection | Second Dose Ferumoxytol injection
(3-8 days after first dose) |
|-----------------------------|-------------|----------------------------------|--|
| Visit Number                | 1           | 2                                | 3  |
| Study Week ( $\pm 7$ days)* | 0           | 0-2                              | 1-3  |
| Informed consent            | X           |                                  |  |
| Screening Evaluation        | X           |                                  |  |
| Medical History             | X           | X                                | X  |
| Bleeding/Blood History      | Transfusion | X                                | X  |

CONFIDENTIAL

This material is the property of the NYU School of Medicine and Langone Medical Center. Do not disclose or use except as authorized in writing by the study sponsor  
Interventional Template Version: 28 APR 2017

|                                |           |   |   |
|--------------------------------|-----------|---|---|
| Vital Signs                    | X         | X | X |
| Cardiovascular exam            | X         | X | X |
| VAD settings                   | X         | X | X |
| Ferumoxytol
Administration* | injection | X | X |
| Infusion Monitoring            |           | X | X |
| AE monitoring                  |           | X | X |
| Concomitant Meds               | X         | X | X |

\*Ferumoxytol injection will be administered according to FDA-approved prescribing instructions 3-8 days apart

CONFIDENTIAL

This material is the property of the NYU School of Medicine and Langone Medical Center. Do not disclose or use except as authorized in writing by the study sponsor  
Interventional Template Version: 28 APR 2017

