### **5.7.2 Handling of Participant Withdrawals or Termination**

Withdrawn or terminated participants will be followed for extraction of clinical data from the medical record for 6 months with participant permission. Since the primary outcome is feasibility, there will be no replacement of withdrawn subjects.

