### Clinical Data Collection for Research

Laboratory data. Clinical blood test results (serum ferritin, transferrin saturation, and hemoglobin) before administration of ferumoxytol injection and from 2-24 weeks after administration of ferumoxytol injection will be recorded by medical chart review.

Bleeding/Transfusion data. Information on bleeding events (source of bleeding, need for hospitalization, intervention(s)) and number of blood transfusion for 2-24 weeks after treatment will be collected from medical chart review.

CONFIDENTIAL

This material is the property of the NYU School of Medicine and Langone Medical Center. Do not disclose or use except as authorized in writing by the study sponsor  
Interventional Template Version: 28 APR 2017

Six-minute walk test. The six-minute walk test is routinely performed in VAD patients for clinical assessment of functional capacity. Results will be obtained by medical chart review.

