## 7.4 Concomitant Medications, Treatments, and Procedures

All concomitant prescription medications taken during study participation will be recorded on the case report forms (CRFs). For this protocol, a prescription medication is defined as a medication that can be prescribed only by a properly authorized/licensed clinician. Medications to be reported in the CRF are concomitant prescription medications, over-the-counter medications and non-prescription medications.

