### **9.3 Analysis Datasets**

Feasibility analysis dataset. Intention to treat (ITT) will be defined as all patients who provide consent and are eligible to receive study treatment. The ITT data set will be used for the primary feasibility endpoint.

Safety objective and exploratory objectives analysis dataset. All eligible subjects who received any study drug, and for whom post-dose data are available, will be included in the safety and exploratory objectives analysis set.

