## **9.4 Description of Statistical Methods**

### **9.4.1 General Approach**

This is a single-arm open label study with a primary feasibility outcome. Descriptive statistics will be used to summarize pertinent characteristics of the study population.

Study Endpoints:

Primary Feasibility Endpoint: The proportion of eligible subjects who complete ferumoxytol injection therapy per study protocol.

Primary Safety Endpoint: The incidence of treatment-related adverse events

Other Exploratory Endpoints:

- Change from pre-treatment baseline in serum ferritin 2-24 weeks after ferumoxytol injection therapy
- Change from pre-treatment baseline in transferrin saturation 2-24 weeks after ferumoxytol injection therapy
- Change from pre-treatment baseline in hemoglobin level 2-24 weeks after ferumoxytol injection therapy
- Change from pre-treatment baseline in 6-minute walk distance 2-24 weeks after ferumoxytol injection therapy

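### The plan has no rule for ferritin, transferrin saturation, hemoglobin or walk values measured after non-study intravenous iron or transfusion, so they count as change after ferumoxytol

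*Combined protocol and SAP*

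**What the plan says.** Section 5.2 excludes at entry anyone with "Treatment with erythropoiesis stimulating agent or intravenous iron in last 3 months". Section 5.4 says of usual practice in the clinic that "iron-deficient patients are routinely referred for intravenous iron infusions as part of standard clinical care". No section restricts non-study intravenous iron or transfusion once study dosing has begun.

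The endpoints in Section 9.4.1 take the form "Change from pre-treatment baseline in hemoglobin level 2-24 weeks after ferumoxytol injection therapy", with matching items for ferritin, transferrin saturation and six-minute walk distance. Section 3.2 lists these changes among the secondary objectives and presents them as effects of the drug relative to baseline. There is no comparator. For the exploratory set, Section 9.3 takes "All eligible subjects who received any study drug, and for whom post-dose data are available". Section 5.7.2 adds that "Withdrawn or terminated participants will be followed for extraction of clinical data from the medical record for 6 months", given the participant's permission. Section 9.4.3 summarises the changes descriptively and does not mention other iron or transfusion. Section 9.2 says the magnitude and variance of these changes will help plan later trials.

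On data capture, the chart-review part of Section 7.1.1 covers iron and hemoglobin results, bleeding events and the walk test, and states that the "number of blood transfusion for 2-24 weeks after treatment will be collected from medical chart review". Non-study intravenous iron is not on that list. The "Concomitant Meds" row of the Schedule of Assessments is marked at Visits 1 to 3 only. Section 7.4 is the general recording rule: "All concomitant prescription medications taken during study participation will be recorded on the case report forms (CRFs".

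**The concern.** The protocol treats recent intravenous iron as important enough to exclude a patient at entry, yet it says nothing about the same treatment once follow-up has started. Follow-up runs to week 24 on routine chart values, in a clinic where other intravenous iron is the usual treatment for iron deficiency and in a population that Section 2.1 describes as prone to gastrointestinal bleeding.

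A value taken after another iron product or a red-cell transfusion reflects that treatment as well as ferumoxytol. In a single-arm study no control group absorbs the difference. The subjects most exposed may be those who received only one dose: they stay in the exploratory set, and they may then receive another product because repletion was not completed. The estimates at stake are the mean and spread of the change in four measures, which the plan intends to carry into the design of later trials.

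**Working it through.** **1. The plan's own figure, for completeness.** Section 9.5 gives more than 80% power for N = 20, null 0.75, alternative 0.40, one-tailed alpha 0.05. An exact lower-tail binomial test rejects at 11 or fewer completers out of 20, with P(X ≤ 11 | 0.75) = 0.0409 and power P(X ≤ 11 | 0.40) = 0.9435. The stated power is met. It concerns completion of treatment, and nothing below changes it.

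**2. One subject followed through the text.** A subject receives dose 1, cannot return, and is terminated under Section 5.7.1. Suppose the subject then has a course of another intravenous iron product (5 to 6 infusions, according to the Protocol Summary) and has chart values at week 10.
- Section 9.3: study drug received and post-dose data available, so the subject is in the exploratory set.
- Section 5.7.2: with permission, chart extraction continues for 6 months, so week 10 is covered.
- Section 9.4.1: week 10 lies between weeks 2 and 24, so the values qualify.
- Section 9.4.3: there is no condition on other treatment, so the values enter the summary.

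A two-dose subject who bleeds, is transfused, and has hemoglobin measured afterwards follows the same path.

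**3. What the analyst would have in hand.**
- Non-study intravenous iron: absent from the Section 7.1.1 list. Section 7.4 may cover it, but the schedule has no collection point after Visit 3.
- Transfusion: a count from week 2 onward. Dates are not requested, and the period between dose 1 and week 2 is outside the count.

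**4. Size, as illustration only.** The documents give no rate of transfusion or non-study iron during follow-up and no effect per event. Let k be the number of subjects out of 20 whose counted hemoglobin value is affected, and d the assumed net change in each. Then shift in mean = (k/20) × d. Percentages are relative to 1.22 and 0.82 g/dL, the largest and smallest mean changes on ferumoxytol in Table I (Section 2.4.2).

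| k | d = 0.5 g/dL | d = 1.0 g/dL | d = 2.0 g/dL |
|---|---|---|---|
| 2 | 0.05 (4–6%) | 0.10 (8–12%) | 0.20 (16–24%) |
| 4 | 0.10 (8–12%) | 0.20 (16–24%) | 0.40 (33–49%) |
| 6 | 0.15 (12–18%) | 0.30 (25–37%) | 0.60 (49–73%) |
| 8 | 0.20 (16–24%) | 0.40 (33–49%) | 0.80 (66–98%) |

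If the bleed outweighs the transfusion, d is negative and each entry changes sign. For scale, the standard error of a mean change at n = 20 with Table I SDs of 1.13 to 1.25 is 1.13/√20 = 0.25 to 1.25/√20 = 0.28 g/dL.

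**5. Spread.** If 4 of 20 values move by d independently of response, variance = 1.24² + 0.2 × 0.8 × d², using the Table I SD of 1.24. For d = 1 this is 1.538 + 0.160 = 1.698 (SD 1.30). For d = 2 it is 1.538 + 0.640 = 2.178 (SD 1.48). Required sample size scales with variance, so a later trial sized on these SDs would need 1.698/1.538 = 1.10 to 2.178/1.538 = 1.42 times as many subjects. This also rests on assumed inputs.

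**The case against.** The endpoints are descriptive with no hypothesis (Section 9.2), and summarising every observed value is a legitimate choice. The middle case of 0.20 g/dL lies within one standard error. Section 7.4 requires medications during study participation to be recorded, and the Protocol Summary counts participation as six months, so intravenous iron is arguably already within the rule. Section 7.1.1 is silent on transfusion dates but does not rule them out, and Section 8.3 records onset times for adverse events, which would date some bleeds. Section 7.3.3 has repletion status reported to the care team after the second dose, which could make an early repeat course less likely in completers.

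These arguments limit the weight of the point but do not remove it. A recording rule with no collection step after Visit 3 is weak assurance, and even complete records would leave unsaid how the affected values are handled.

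Several stronger inferences are tempting, and the documents do not support them:
- **Transfusion is routine, or either treatment is expressly allowed after dosing.** Only intravenous iron is called routine. For transfusion there is a planned count and a raised bleeding risk. The absence of a restriction is silence, not permission.
- **Sections 2.4.1 and 7.1.2 show subjects being sent for other iron after dosing.** Both describe patients who are not in the study. The nine earlier recipients in Section 2.1 are a count with no time frame and give no rate.
- **Erythropoiesis-stimulating agents are a comparable source of contamination.** Section 2.1 calls them contraindicated in these patients.
- **Five of 20 subjects would be one-dose subjects.** That is 0.25 × 20 at the null, not an expectation. The intention-to-treat set can also include eligible subjects who receive no dose, and they are outside the exploratory set.
- **The response is overstated.** The direction is unknown, because bleeding can outweigh transfusion.

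**Conclusion.** The point holds as a gap in the exploratory analysis. Followed as written, the plan counts values measured after non-study intravenous iron or transfusion as change after ferumoxytol, and it does not secure the dated information needed to examine them separately. The primary feasibility endpoint, its power and the safety endpoint are unaffected.

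The size and sign of the bias cannot be derived from the documents. The range of 0.05 to 0.80 g/dL in mean hemoglobin (4% to 98% of the Table I changes) depends entirely on assuming 2 to 8 affected subjects out of 20 and a net change of 0.5 to 2.0 g/dL in each, in either direction. No figure is offered for ferritin, transferrin saturation or walk distance. A reader might conclude that the treatments could never be separated afterwards. That is not established, since Section 7.4 and the adverse event records may supply part of the information. The change is best classed as a cheap improvement, worth making because the estimates are meant for planning later trials.

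**What to change.** Make no change to care. Four additions are enough:
1. In Section 7.1.1, abstract each administration of non-study intravenous iron and each transfusion, with its date, from dose 1 to week 24.
2. In Section 9.4.3, keep the summary of all observed values and add a second summary that leaves out values after a subject's first non-study intravenous iron or transfusion. State that this exclusion may be informative: it can keep a pre-bleed hemoglobin and drop the later fall, and a subject with an early event may have no value. For that reason it should accompany the full summary and not replace it.
3. Show one-dose and two-dose subjects separately.
4. Report how many subjects had each type of event.

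The cost is a few extra chart-review fields for 20 subjects and a short addition to Section 9.4.3. The second summary will rest on fewer, possibly selected, values. Sample size and the primary analysis stay as they are.

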### **5.5 Duration of Study Participation**

The study will require active participation at three visits conducted over 1-3 weeks. The screening visit and first injection of study drug may occur on the same day. Clinical data from the medical record will be reviewed and entered in the research database for 6 months. There are no study procedures other than data collection from medical record after completion of the two visits for study drug infusion.

### **5.6 Total Number of Participants and Sites**

Recruitment will end when 20 participants are enrolled. It is expected that 20 participants will be enrolled in order to produce 20 evaluable participants.

### **5.7 Participant Withdrawal or Termination**

#### **5.7.1 Reasons for Withdrawal or Termination**

CONFIDENTIAL

This material is the property of the NYU School of Medicine and Langone Medical Center. Do not disclose or use except as authorized in writing by the study sponsor  
Interventional Template Version: 28 APR 2017

Participants are free to withdraw from participation in the study at any time upon request. An investigator may terminate participation in the study if:

- Any clinical adverse event (AE), laboratory abnormality, or other medical condition or situation occurs such that continued participation in the study would not be in the best interest of the participant
- The participant meets an exclusion criterion (either newly developed or not previously recognized) that precludes further study participation
- The participant is not able to return for the second dose of ferumoxytol within 15 days of the first dose.

### **5.7.2 Handling of Participant Withdrawals or Termination**

Withdrawn or terminated participants will be followed for extraction of clinical data from the medical record for 6 months with participant permission. Since the primary outcome is feasibility, there will be no replacement of withdrawn subjects.

### **5.8 Premature Termination or Suspension of Study**

This study may be temporarily suspended or prematurely terminated if there is sufficient reasonable cause. Written notification, documenting the reason for study suspension or termination, will be provided by the principal investigator. If the study is prematurely terminated or suspended, the PI will promptly inform the IRB and will provide the reason(s) for the termination or suspension.

Circumstances that may warrant termination or suspension include, but are not limited to:

- Determination of unexpected, significant, or unacceptable risk to participants
- Insufficient compliance to protocol requirements
- Data that are not sufficiently complete and/or evaluable
- Determination of futility

## **6 Study Agent (Study drug, device, biologic, vaccine etc.) and/or Procedural Intervention**

### **6.1 Study Agent Description**

Ferumoxytol injection, an iron replacement product, is a non-stoichiometric magnetite (superparamagnetic iron oxide) coated with polyglucose sorbitol carboxymethylether. The overall colloidal particle size is 17-31 nm in diameter. The chemical formula of ferumoxytol injection is  $\text{Fe}_{5874}\text{O}_{8752} \cdot \text{C}_{11719}\text{H}_{18682}\text{O}_{9933}\text{Na}_{414}$  with an apparent molecular weight of 750 kDa.

Ferumoxytol injection is an aqueous colloidal product that is formulated with mannitol. It is a black to reddish brown liquid, and is provided in single use vials containing 510 mg of elemental iron. Each mL of the sterile colloidal solution of ferumoxytol injection contains 30 mg of elemental iron and 44 mg of mannitol, and has low bleomycin-detectable iron. The formulation is isotonic with an osmolality of 270-330 mOsm/kg. The product contains no preservatives, and has a pH of 6 to 8.

CONFIDENTIAL

Ferumoxytol injection consists of a superparamagnetic iron oxide that is coated with a carbohydrate shell, which helps to isolate the bioactive iron from plasma components until the iron-carbohydrate complex enters the reticuloendothelial system macrophages of the liver, spleen and bone marrow. The iron is released from the iron-carbohydrate complex within vesicles in the macrophages. Iron then either enters the intracellular storage iron pool (e.g., ferritin) or is transferred to plasma transferrin for transport to erythroid precursor cells for incorporation into hemoglobin.

Ferumoxytol injection Injection is available in single use vials. Each vial contains 510 mg of elemental iron in 17 mL (30 mg per mL).

Use of ferumoxytol injection in this study meets criteria for IND exemption, since all of the following conditions apply:

- (i) the investigation is not intended to be reported to FDA as a well-controlled study in support of a new indication for use nor intended to be used to support any other significant change in the labeling for the drug;
- (ii) Ferumoxytol injection is lawfully marketed as a prescription drug product; the investigation is not intended to support a significant change in the advertising for the product;
- (iii) the investigation does not involve a route of administration or dosage level or use in a patient population or other factor that significantly increases the risks (or decreases the acceptability of the risks) associated with the use of the drug product;
- (iv) the investigation is conducted in compliance with the requirements for review by an IRB (21CFR56) and the requirements for informed consent (21CFR 50); and
- (v) the investigation is conducted in compliance with the requirements of 21CFR312.7 (Promotion and sale of investigational drugs).

### **6.1.1 Acquisition**

Investigational product will be obtained from the US manufacturer of ferumoxytol injection (AMAG pharmaceuticals).

